#### 8.21 Lenalidomide dose adjustment for renal function

Lenalidomide dose will be adjusted as per standard of care guidelines in the prescribing information of lenalidomide for multiple myeloma patients.

8.3 Daratumumab Dose Modifications (**NOTE:** Only if any of the following criteria are met and the event cannot be ascribed to lenalidomide or to any other concurrent medication that the patient may be on, the daratumumab administration must be held/omitted as specified below to allow for recovery from toxicity).

→ → **Use the NCI Common Terminology Criteria for Adverse Events (CTCAE) version 4.0\***  

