### 8.0 Dosage Modification Based on Adverse Events

Any adverse event noted in the study and its resultant dose-modifications should be managed as per the prescribing information of daratumumab and/or lenalidomide as per which of these two drugs the adverse event is attributable to.

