**ALERT:** **ADR reporting may be required for some adverse events (See Section 10)**

#### 8.1 General Considerations:

- Missed doses for lenalidomide are to be omitted rather than made up, unless the dose was forgotten and remembered on the same day, in which case the dose can be taken

that day. Any doses missed on a particular day are not to be made up the next day. Doses that are considered to be vomited are not to be made up and a mention about the time of dose and time of vomiting episode should be made in the pill diary.

- b) Daratumumab may be administered within  $\pm 1$  day of the scheduled dose if there are any logistical challenges (holiday, patient transport or other logistics, scheduling availability, etc.)
- c) If multiple toxicities are experienced, dose modifications will be based on the toxicity requiring the largest dose reduction.
- d) Reductions are based on the dose given in the preceding cycle and are based on toxicities with an attribution of possible, probable, or definite that were observed since the prior toxicity evaluation.
- e) If a drug is omitted due to specific adverse events and the patient is on combination therapy (maintenance therapy), the other agents, considered unrelated to the adverse event may be continued.
- f) If a patient cannot be administered a dose of daratumumab during Consolidation 1 (Cycles 1-2 or 1-4, as the case may be for that patient) for  $>28$  days due to adverse events or any other reason, the patient should be removed from the study treatment and go to event monitoring. (NOTE: Patients on maintenance therapy (cycles 4 and beyond, or cycle 6 and beyond as the case may be for that patient) may be continued on treatment with single-agent daratumumab or lenalidomide in case the other agent has to be permanently discontinued in absence of disease progression. If a patient on maintenance treatment must discontinue both, lenalidomide and daratumumab, they should be removed from the protocol therapy and proceed to event monitoring.

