## 8.2 Lenalidomide Dose Modifications

Lenalidomide (Days 1-21)	
Starting dose	10mg
-1	5 mg
-2	Discontinue

→ → Use the NCI Common Terminology Criteria for Adverse Events (CTCAE) version 4.0\*  
unless otherwise specified ← ←

CTCAE System/Organ/Class (SOC)	ADVERSE EVENT	AGENT	ACTION**

CTCAE System/Organ/Class (SOC)	ADVERSE EVENT	AGENT	ACTION**
Investigations	Platelet count decreased Grade 4	Lenalidomide	
*Omit dose until AE has resolved to Grade 1 or better
 
 
• Follow CBC weekly
 
• If thrombocytopenia <math><30,000/\text{mm}^3</math> recurs, reduce dose by one dose level (by 5 mg) and continue therapy when platelet count <math>\geq 30,000/\text{mm}^3</math>
 
 
If, after lenalidomide has been omitted, and the AE does not return to <math>\leq</math>Grade 1 within 4 weeks, then the patient may continue on single-agent daratumumab till the completion of maintenance and then proceed to Event Monitoring

	Neutrophil count decreased Grade 4		
*Omit dose until AE has resolved to Grade 2 or better
 
 
• Follow CBC weekly
 
* If neutropenia has resolved to <math>\leq</math>Grade 2, resume dose at one level lower
 
* If, after lenalidomide has been omitted, and the AE does not return to <math>\leq</math>Grade 1 within 4 weeks, then the patient may continue on single-agent daratumumab till the completion of maintenance and then proceed to Event Monitoring
 

Blood and lymphatic system disorders	Anemia Grade 4		
*Omit dose until AE has resolved to Grade 2 or better
 
 
• Follow CBC weekly
 
* If anemia has resolved to <math>\leq</math>Grade 2, resume dose at one level lower
 
* If, after lenalidomide has been omitted, and the AE does not return to <math>\leq</math>Grade 1 within 4 weeks, then the patient may continue on single-agent daratumumab till the completion of maintenance and then proceed to Event Monitoring
 

	Febrile neutropenia $\geq$ Grade 3		
 
• Omit dose and follow CBC weekly
 
• If neutropenia has resolved to <math>\leq</math>Grade 2, resume dose at same level with GCSF support (See Section 9.6)
 

CTCAE System/Organ/Class (SOC)	ADVERSE EVENT	AGENT	ACTION**

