**unless otherwise specified ← ←**

CTCAE System/Organ/Class (SOC)	ADVERSE EVENT	AGENT	ACTION**
Investigations	Neutrophil count decreased Grade 4 lasting >7 days	Daratumumab	Hold (Day 1) or Omit (Days 8, 15, or 22) Daratumumab ** until recovery to Grade ≤2 or baseline May restart at same dose at the next planned dosing date.
	Platelet count decreased Grade ≥3 with bleeding		
Blood and lymphatic system disorders	Febrile neutropenia ≥Grade 3		Hold (Day 1) or Omit (Days 8, 15, or 22) Daratumumab ** until recovery to Grade ≤2 or baseline May restart at same dose at the next planned dosing date.
	Neutropenia with infection, of any grade		
Gastrointestinal disorders	Nausea Grade 2 (if persistent for >7 days despite optimal antiemetic therapy)		Hold (Day 1) or Omit (Days 8, 15, or 22) Daratumumab ** until recovery to Grade ≤1 or baseline May restart at same dose at the next planned dosing date.
	Vomiting ≥Grade 3 (if persistent for >7 days despite optimal antiemetic therapy)		
	Diarrhea ≥Grade 3 (if persistent for >7 days despite optimal anti-diarrheal therapy)		
Other (Non-hematologic)****	Any other Grade 4 AE or any unmanageable Grade 3 AE that was present at baseline or lasts for >7 days after the last administration of daratumumab		Hold (Day 1) or Omit (Days 8, 15, or 22) Daratumumab ** until recovery to Grade ≤1 or baseline May restart at same dose at the next planned dosing date.

Additional Adverse Events:

\*\* If Daratumumab is omitted in the middle of the cycle and the toxicity resolves, patient can re-start the drug but the days of drug treatment missed do not need to be caught-up and can be omitted in order to maintain the cycle schedule.

- Dose omission: Daratumumab may be omitted for adverse event considerations for a maximum of 28 consecutive days during Consolidation 1 (Cycle 1-2 or 1-4, as the case may be for that patient). Patients on maintenance therapy may be continued on treatment with single-agent daratumumab or lenalidomide in case the other agent has to be permanently discontinued in absence of disease progression. If a patient on maintenance treatment must discontinue both,

lenalidomide and daratumumab, they should be removed from the protocol therapy and proceed to event monitoring.

- If multiple adverse events are seen, administer dose based on the greatest reduction required by any single adverse event observed.

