**Less common known potential toxicities, 1% - 10%:**

Cardiovascular: Edema, deep vein thrombosis, hypertension, chest pain, palpitation, atrial fibrillation, syncope

Central nervous system: Insomnia, hypoesthesia, pain, depression

Dermatologic: Brusing, cellulitis, erythema

Endocrine & metabolic: Hypothyroidism, hypomagnesemia, hypocalcemia

Gastrointestinal: Vomiting, xerostomia, loose stools

Genitourinary: Dysuria

Hematologic: Leukopenia, febrile neutropenia, Lymphopenia

Hepatic: ALT increased

Neuromuscular & skeletal: Myalgia, rigors, neuropathy

Respiratory: Sinusitis, rhinitis, bronchitis, pulmonary embolism

Miscellaneous: Night sweats, diaphoresis

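### The Section 8.3 note ties the mandatory daratumumab hold to an attribution test that disagrees with 8.0, 8.1 and 15.18 when an event may be due to both drugs

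*Combined protocol and SAP*

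**What the plan says.** The note at the head of Section 8.3 has two conditions. One of the tabulated criteria must be met, and it must be that "the event cannot be ascribed to lenalidomide or to any other concurrent medication that the patient may be on". When both hold, "the daratumumab administration must be held/omitted as specified below to allow for recovery from toxicity".

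Five other places in the protocol bear on the same decision:

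- **Section 8.0:** any adverse event "should be managed as per the prescribing information of daratumumab and/or lenalidomide as per which of these two drugs the adverse event is attributable to".
- **Section 8.1d:** reductions "are based on toxicities with an attribution of possible, probable, or definite".
- **Section 8.1e:** when one drug is omitted during combination therapy, "the other agents, considered unrelated to the adverse event may be continued".
- **Attribution bullet below the 8.3 table:** dose modifications are tied to events attributed to study treatment, and only events judged unrelated or unlikely related are exempted.
- **Section 15.18 (daratumumab nursing guidelines):** patients with an ongoing infection should not be given the drug. No attribution condition is attached.

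**The concern.** Lenalidomide and daratumumab are given together in Cycles 4-15 (or 6-17), and their listed toxicities overlap heavily. An event judged possibly related to both drugs is therefore an ordinary case. Section 8.0 foresees it and directs management by each implicated drug. The 8.3 note, read literally, removes the mandatory daratumumab hold once lenalidomide, or any other concurrent medication, is a candidate cause. Section 7.13 requires thromboprophylaxis for every patient on maintenance, so for a bleeding event there is always a further concurrent drug to consider.

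Two investigators with the same patient could each follow the protocol and act differently, depending on which paragraph they read. The matter at stake is patient safety. For some events the lenalidomide table offers no action either.

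**Working it through.** No sample size, error rate or event count enters this point. The check compares the texts and then matches each 8.3 trigger with the toxicity lists and with the lenalidomide table.

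**Step 1: the rules by type of attribution**

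- *Daratumumab only:* the note is satisfied and the 8.3 table applies. No conflict.
- *Lenalidomide only:* the note is not satisfied. 8.0 points to lenalidomide, and 8.1e allows daratumumab to continue. No conflict on attribution, except that 15.18 still withholds daratumumab if an infection is ongoing.
- *Both drugs:* the note is not satisfied, so no hold is mandatory. 8.0 points to both drugs. Daratumumab is not an agent considered unrelated, so the 8.1e permission to continue does not reach it. The event is attributed to study treatment, so the exemption in the 8.3 bullet does not reach it either. The note therefore stands apart from the other texts, including a bullet in its own section.

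Section 10.3 grades attribution in five categories, and the note's term (ascribed) is not one of them. It could mean possible or higher, or something stronger. Under either meaning the conflict remains for an event definitely related to lenalidomide and possibly related to daratumumab.

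**Step 2: the 8.3 triggers against Section 15 and Section 8.2**

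| Trigger named in 8.3 | Underlying toxicity listed for lenalidomide (15.27) | Listed for daratumumab (15.15) | Row in 8.2 if ascribed to lenalidomide |
|---|---|---|---|
| Grade 4 neutrophil decrease beyond 7 days | Yes | Yes | Yes (Grade 4) |
| Grade 3 or higher platelet decrease with bleeding | Yes | Yes | Grade 4 only |
| Febrile neutropenia, Grade 3 or higher | Yes | Yes | Yes |
| "Neutropenia with infection, of any grade" | Yes | Yes | Only if Grade 4 or febrile |
| Nausea, Grade 2, beyond 7 days | Yes | Yes | None |
| Vomiting, Grade 3 or higher, beyond 7 days | Yes | Yes | Residual row |
| Diarrhea, Grade 3 or higher, beyond 7 days | Yes | Yes | Residual row |

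The platelet entry in 8.2 is "Platelet count decreased Grade 4"; its instruction on recurrence comes into play only after that first event. Febrile neutropenia is on the lenalidomide list under "Leukopenia, febrile neutropenia, Lymphopenia". The residual row in 8.2 covers only non-hematologic events of Grade 3 or higher assessed as related to lenalidomide. It therefore reaches the platelet and infection triggers only when the bleeding or the infection is itself Grade 3 or higher.

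**Step 3: counts**

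- Triggers whose underlying toxicity is listed for both drugs: 7 of 7.
- Triggers with some events that have no 8.2 row: 3 of 7. These are Grade 3 platelets with bleeding below Grade 3, Grade 1-3 non-febrile neutropenia with infection below Grade 3, and persistent Grade 2 nausea. The other 7 - 3 = 4 are matched.
- Daratumumab doses scheduled in combination: Cycles 1-2 give 4 x 2 = 8 and combined maintenance gives 12, so 12/20 = 60% through Cycle 15. With optional Cycles 3-4 (2 x 2 = 4), 12/24 = 50% through Cycle 17. Single-agent doses after that are not counted.

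**The case against.** The strongest reply is that the note only says when a hold must occur. It does not forbid a discretionary hold, and 8.0 sends the investigator to the prescribing information in any case. This stands: a reader might infer that the protocol bars a pause, and the text does not say so. Because the prescribing information is not part of the documents, it also cannot be shown that no action would follow.

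The clash with 8.1 is softer than it looks. 8.1d speaks of reductions, while the 8.3 table has none for daratumumab, only hold or omit and restart at the same dose. So 8.1d shows a mismatch of attribution thresholds and not a direct contradiction. 8.1e is permissive, agrees with the note when lenalidomide alone is the cause, and diverges from it only by implication. These points also stand. They do not touch the conflict with 8.0, or the 8.3 bullet, which speaks of modifications in general.

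A specific rule may qualify a general one, and treating lenalidomide as the first suspect could be deliberate. The documents do not say so, and the bullet within 8.3 points the other way.

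Finally, safeguards exist outside the table. 15.18 withholds daratumumab during any ongoing infection, so it would be wrong to conclude that a patient with neutropenia and infection receives full treatment under the protocol. The text below the 8.3 table separately omits all study drugs for clotting events. The first safeguard is itself one more passage that the note does not agree with.

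**Conclusion.** The inconsistency is real and confined to shared attribution. The note conflicts with 8.0, does not match 8.1d, 8.1e or the 8.3 bullet, and disagrees with 15.18 on infection. No passage states how an event attributable to both drugs is handled. In combined maintenance each of the 7 named triggers can fall outside the mandatory hold, and for 3 of them some events would have no 8.2 row either if ascribed to lenalidomide. This rests on a literal reading of the note and on the toxicity lists in Section 15.

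Two stronger readings are not supported:

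- A reader might infer that the daratumumab triggers are disabled, or the table inactive, throughout combined maintenance. Overlap of 7 of 7 shows that a trigger can be blocked, not that it will be. Attribution is judged event by event, and the table still applies when no other drug is held responsible. The 60% and 50% are shares of doses given in combination and do not measure how often the table fails.
- A reader might infer damage to the dose exposure behind safety objective 2.24. Section 16.42 plans tables of maximum grade with relationship considered, and no dose-exposure analysis.

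Nothing here alters the sample size, significance level or power in Section 16.

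**What to change.** Reconcile the 8.3 note with 8.0, 8.1d, 8.1e, the attribution bullet below the 8.3 table and 15.18, so that one attribution standard, preferably in the five categories of Section 10.3, states how an event attributable to both drugs is handled. Then check that every 8.3 trigger has a stated action in combined maintenance when it is ascribed to lenalidomide, starting with the three unmatched cases in the table above. Which rule applies is for the sponsor to decide.

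The cost is protocol wording. Depending on the rule chosen, a few more attribution decisions may end in a recorded hold.

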**unless otherwise specified ← ←**

CTCAE System/Organ/Class (SOC)	ADVERSE EVENT	AGENT	ACTION**
Investigations	Neutrophil count decreased Grade 4 lasting >7 days	Daratumumab	Hold (Day 1) or Omit (Days 8, 15, or 22) Daratumumab ** until recovery to Grade ≤2 or baseline May restart at same dose at the next planned dosing date.
	Platelet count decreased Grade ≥3 with bleeding		
Blood and lymphatic system disorders	Febrile neutropenia ≥Grade 3		Hold (Day 1) or Omit (Days 8, 15, or 22) Daratumumab ** until recovery to Grade ≤2 or baseline May restart at same dose at the next planned dosing date.
	Neutropenia with infection, of any grade		
Gastrointestinal disorders	Nausea Grade 2 (if persistent for >7 days despite optimal antiemetic therapy)		Hold (Day 1) or Omit (Days 8, 15, or 22) Daratumumab ** until recovery to Grade ≤1 or baseline May restart at same dose at the next planned dosing date.
	Vomiting ≥Grade 3 (if persistent for >7 days despite optimal antiemetic therapy)		
	Diarrhea ≥Grade 3 (if persistent for >7 days despite optimal anti-diarrheal therapy)		
Other (Non-hematologic)****	Any other Grade 4 AE or any unmanageable Grade 3 AE that was present at baseline or lasts for >7 days after the last administration of daratumumab		Hold (Day 1) or Omit (Days 8, 15, or 22) Daratumumab ** until recovery to Grade ≤1 or baseline May restart at same dose at the next planned dosing date.

Additional Adverse Events:

\*\* If Daratumumab is omitted in the middle of the cycle and the toxicity resolves, patient can re-start the drug but the days of drug treatment missed do not need to be caught-up and can be omitted in order to maintain the cycle schedule.

- Dose omission: Daratumumab may be omitted for adverse event considerations for a maximum of 28 consecutive days during Consolidation 1 (Cycle 1-2 or 1-4, as the case may be for that patient). Patients on maintenance therapy may be continued on treatment with single-agent daratumumab or lenalidomide in case the other agent has to be permanently discontinued in absence of disease progression. If a patient on maintenance treatment must discontinue both,

lenalidomide and daratumumab, they should be removed from the protocol therapy and proceed to event monitoring.

- If multiple adverse events are seen, administer dose based on the greatest reduction required by any single adverse event observed.
- Dose modifications are for adverse events attributed to study treatment only. Dose modifications are not required for adverse events if they are deemed unrelated and/or unlikely related to study treatment.
- Reductions apply to treatment given in the preceding cycle and are based on adverse events observed since the prior dose.

\*\*\*\* If cough, dyspnea, and other pulmonary symptoms occur, a chest x-ray and high-resolution chest CT scan should be obtained. Incentive spirometry studies (to include DLCO) should be considered. Consider Pneumocystis pneumonia or viral pneumonitis. Patients who experience a deep vein thrombosis (DVT), pulmonary embolus (PE), or other clotting event should have all study drugs temporarily omitted while full-dose anticoagulation is initiated (other than warfarin or other Vitamin K antagonist). There should not be a delay of more than 28 days in reinitiating the study treatment.

**NOTE:** If the patient experiences a significant adverse event requiring a dose reduction at the start of the next cycle, then the dose will remain lowered for that entire remaining length of the study treatment.

**NOTE:** In the event patient is benefitting from treatment and the delay was unrelated to treatment toxicity, patient may remain on study with approval of study PI.

## 9.0 Ancillary Treatment/Supportive Care

### 9.1 Full Supportive Care

Patients should receive full supportive care while on this study. This includes blood product support, antibiotic treatment, and treatment of other newly diagnosed or concurrent medical conditions. All blood products and concomitant medications such as antidiarrheals, analgesics, and/or antiemetics received from the first day of study treatment administration until 30 days after the final dose will be recorded in the medical records.

### 9.2 Bisphosphonates

Patients may receive concurrent treatment with a bisphosphonate.

### 9.3 Thromboprophylaxis

Due to the increased risk of deep vein thrombosis (DVT) for multiple myeloma patients, thromboprophylaxis is to be used as standard of care on this regimen according to the International Myeloma Working Group guidelines (<http://jco.ascopubs.org/content/32/6/587.full>).

### 9.4 Prohibited medications

The following medications are not permitted during the trial:

- Any other investigational treatment
- Any cytotoxic chemotherapy

- Any other systemic anti-neoplastic therapy including, but not limited to, immunotherapy, hormonal therapy or monoclonal antibody therapy.
- Any external beam radiotherapy. **NOTE:** Radiation therapy administered with palliative intent to control localized symptoms from MM is permitted provided the symptoms are not considered due to disease progression.

#### 9.5 Anti-emetics

Anti-emetics may be used at the discretion of the attending physician

#### 9.6 Blood products and growth factors

Blood products and growth factors should be utilized as clinically warranted and following institutional policies and recommendations. The use of growth factors should follow published guidelines of the American Society of Clinical Oncology (42) Update of Recommendations for the Use of Hematopoietic Colony-Stimulating Factors: Evidence-Based, Clinical Practice Guidelines.

#### 9.7 Diarrhea

Diarrhea could be managed conservatively with loperamide. The recommended dose of loperamide is 4 mg at first onset, followed by 2 mg every 2-4 hours until diarrhea free (maximum 16 mg/day).

In the event of Grade 3 or 4 diarrhea, the following supportive measures are allowed: hydration, octreotide, and antidiarrheals.

If diarrhea is severe (requiring intravenous rehydration) and/or associated with fever or severe neutropenia (grade 3 or 4), broad-spectrum antibiotics must be prescribed. Patients with severe diarrhea or any diarrhea associated with severe nausea or vomiting **should be hospitalized** for intravenous hydration and correction of electrolyte imbalances.

#### 9.8 Concomitant medications

Any systemic, anti-myeloma therapy or steroids other than those prescribed by the protocol are prohibited while on protocol therapy. Guidelines for selection and use of other concomitant medications should be derived from the lenalidomide and daratumumab prescribing information. Other than study medications, administration of any therapeutic or diagnostic investigational agent (for any indication) is prohibited while on study.

### 10.0 Adverse Event (AE) Reporting and Monitoring

The site principal investigator is responsible for reporting any/all serious adverse events to the sponsor as described within the protocol, regardless of attribution to study agent or treatment procedure.

The sponsor/sponsor-investigator is responsible for notifying FDA and all participating investigators in a written safety report of any of the following:

- Any suspected adverse reaction that is both serious and unexpected.
- Any findings from laboratory animal or *in vitro* testing that suggest a significant risk for human subjects, including reports of mutagenicity, teratogenicity, or carcinogenicity.

- Any findings from epidemiological studies, pooled analysis of multiple studies, or clinical studies, whether or not conducted under an IND and whether or not conducted by the sponsor, that suggest a significant risk in humans exposed to the drug
- Any clinically important increase in the rate of a serious suspected adverse reaction over the rate stated in the protocol or Investigator's Brochure (IB).

Summary of SAE Reporting for this study  
(please read entire section for specific instructions):

WHO:	WHAT form:	WHERE to send:
All sites	Pregnancy Reporting http://ctep.cancer.gov/protocolDevelopment/electronic_applications/docs/PregnancyReportFormUpdated.pdf	Mayo Sites – attach to MCCC Electronic SAE Reporting Form
Mayo Clinic Sites	Mayo Clinic Cancer Center SAE Reporting Form http://livecycle2.mayo.edu/workspace/?startEndpoint=MC4158-56/Processes/MC4158-56-Process.MC4158-56 AND attach MedWatch 3500A: http://www.fda.gov/downloads/AboutFDA/ReportsManualsForms/Forms/UCM048334.pdf	Will automatically be sent to [contact]

